5.2 Muscle Stretching/Strengthening (i.e., Physical Conditioning) Control Program

Overview and rationale: This trial will include a 12-week non-specific muscle stretching/strengthening program that will provide a rigorous time-and-attention control for the yoga program, but has been designed to avoid engaging the pelvic floor or promoting mindful relaxation. To minimize differential expectations of treatment success, women will be told that they are enrolling in a study of two different types of low-impact physical activity-based interventions (yoga versus physical conditioning) to enhance management of incontinence. Control group exercises have been adapted from exercises used in prior studies conducted by the investigators, such as the PRYSMS trial of restorative yoga vs. stretching for metabolic syndrome (designed by [name], DPT, consultant on this proposal), and pilot-tested in the investigators' prior pilot study of yoga versus physical conditioning for women with incontinence. Similar to postures in the yoga program, the exercises in the stretching/strengthening program have been selected for their potential to be performed safely by women across a range of ages and flexibility levels.

Content and exercises: After a brief education about sitting and standing posture,

the control intervention program will focus on a core set of muscle stretching and strengthening exercises that will be performed sitting in a chair: levator scapulae, upper trapezius, scalenes, shoulder horizontal adduction, triceps, pectoral stretch with hands behind head, wrist flexors and extensors, trunk flexion, trunk extension, trunk side-bend, trunk rotation, and hamstring stretches. Additional chair exercises will incorporate a stretching strap: pectoral stretch with strap, gastrocnemius stretch with strap, and hand behind back with strap. A few stretches will be performed on an exercise mat on the floor: supine single knee to chest, supine hamstrings stretch with strap, quadriceps stretch with strap, supine shoulder flexion with stretch strap, and seated adductor stretch. Several exercises will be performed in the standing position: gastrocnemius, soleus, shoulder flexion, and shoulder abduction stretches.

Staff qualifications and training: Each stretching/strengthening class series will be led by a primary instructor who: 1) is either certified as a personal trainer through the National Academy of Sports Medicine, National Strength and Conditioning Association, or the American College of Sports Medicine, or National Strength and Conditioning Association (NSCA), or licensed as a physical therapist by the Physical Therapy Board of California; 2) has at least 2 years of experience working as a physical therapist or physical trainer in either individual or group settings; 3) will have reviewed a detailed, study-specific training manual describing all of the stretching/strengthening exercises to be used in the study program; 4) will have completed at least 2 hours of in-person training in study-specific techniques with study expert consultant; 5) will have completed additional study-specific training in clinical trial procedures, documentation of participant attendance, review of home practice logs (for adherence), and recording of exercises performed during group classes on appropriate study forms; 6) carries and submits proof of personal liability insurance (minimum of \$2 million coverage); 7) confirms his or her willingness to adhere to the study intervention procedures. For each class series, a back-up instructor will also be identified who can teach a class in the event that the primary instructor is ill or is unable to teach due to an emergency.

Group orientation and classes: Similar to the yoga program, the stretching/strengthening control program will begin with a group orientation led by a physical therapist/trainer, who will provide an overview of the stretching/strengthening exercises to be covered in the program. This will be followed by 90-minute twice weekly group classes, each with no more than 15 participants, led by the same therapist/trainer, who will have received in-person study-specific training from a study expert physical therapist consultant. Classes will be designed to make women comfortable with all exercises by 6 weeks and fully confident in performing exercises by 12 weeks. During the COVID-19 pandemic, classes may be converted to remote platforms (i.e., may take the form of interactive on-line video-based classes rather than in-person classes).

Home practice: In addition to attending group classes, women will be asked to perform stretching/strengthening exercises at home at least one additional hour per week and record the dates and times of practice in a log. Women will receive a detailed manual with pictures and descriptions of each stretching/strengthening exercise to guide them in home practice, as well as a stretch strap and exercise mat to use at home.

Quality and safety: Instructors leading physical conditioning classes will be physical therapists or trainers who have at least 2 years of experience working with adults of a range of ages and have completed dedicated in-person training with [name], DPT. [name] will provide quality monitoring and assess women's success in learning stretching/strengthening exercises by making an in-person visit to at least one class in each series. She will also lead twice monthly conference calls with instructors, similar to quality monitoring for the yoga program.

Post-intervention program continuation: After the end of the main 12-week intervention period, participants will be encouraged to continue practice stretching/strengthening exercises at least two hours per week at home, although group intervention classes will no longer be offered through the study.

5.3 Concomitant Interventions

5.3.1 Required Interventions

Participants in both intervention groups will also receive a pamphlet at the Baseline Clinic Visit that provides basic patient-directed information about first-line behavioral self-management of incontinence, including pelvic muscle exercises, timed urination, and urge suppression. This pamphlet is consistent with usual care of incontinence in the general community, and has been used in previous studies of experimental treatments for incontinence conducted by the investigators.⁴⁵ Participants will be queried about use of these techniques at baseline, at the 6-week and 12-week clinic visits, and as part of the 12- and 24-week post-intervention assessment, so that information about co-interventions can be incorporated into data analyses if appropriate.

Since information about behavioral self-management of incontinence is available from multiple websites and public resources, systematic provision of this information will help avoid differential use of self-management techniques between treatment groups, and will also reflect expected concomitant use of these techniques with yoga in clinical practice. However, participants will be discouraged from pursuing more formal training or coaching in behavioral incontinence treatment strategies from pelvic floor physical therapists or other specialized healthcare practitioners during the trial intervention period (see prohibited interventions below).

5.3.2 Prohibited or Discouraged Interventions

Participants will be asked to refrain from using other standard clinical treatments for incontinence during the 12-week intervention period. These include medications with the potential to affect incontinence (anticholinergic bladder medications, tricyclic antidepressants, mirabegron), invasive or surgical bladder treatments, nerve stimulation therapy, medical devices used to improve bladder symptoms (e.g., pessary), and behavioral treatment programs administered by certified practitioners (e.g., pelvic floor rehabilitation therapy, biofeedback programs).

Participants will be queried about use of these treatments at baseline, at the 6-week and 12-week clinic visits. If participants are found to be using these treatments during the 12-week study intervention period, they will not be required to terminate the study early, but use of outside treatment will be recorded as a protocol deviation, and information about use of these additional treatments may be taken into account in per protocol data analyses.

During the 12- and 24-week post-intervention follow-up periods, participants will also be encouraged to avoid using other clinical treatments for incontinence, and instead focus on continued home practice of study yoga or muscle stretching/strengthening exercises to manage their symptoms.

Participants will be queried about use of these treatments at the 12- and 24-week follow-up assessments, so that information about use of these treatments can be incorporated into data analyses. However, use of other clinical incontinence treatments during the 12- and 24-week post-intervention follow-up periods will not be considered a protocol deviation.

Additionally, participants will be asked to refrain from starting or changing the dosage of medications that could affect depression or anxiety symptoms (e.g., antidepressants, sedatives/hypnotics, or antipsychotic agents) during the 12-week intervention period or 12- or 24-week post-intervention follow-up period, although maintenance of stable dosages of these medications will be acceptable.

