introduce postures as classes progress, with the goal of making participants comfortable with all core postures by the end of 6 weeks and fully confident in performing postures by 12 weeks. During the COVID-19 pandemic, class instruction may be converted to remote platforms (i.e., may take the form of interactive on-line video-based classes rather than in-person classes).

Home practice: In addition to attending group classes, participants will be asked to practice yoga at home at least one additional hour per week and will be given a diary to keep track of the dates and times of practice. Women will also be given a written manual, pre-tested in the investigators' pilot studies, that includes pictures and descriptions of each yoga posture to guide them in home practice. Each participant will be given a limited set of yoga props (a mat, belt, and 2 blocks) for home practice. Women will be encouraged to practice with other members of their classes, but will be discouraged from practicing with individuals who are not in their class and from taking part in non-study yoga activities that might dilute study techniques.

Quality and safety: The study program will incorporate multiple modifications to help women across the age range to perform postures in ways that minimize risk of muscle strain or injury. Participant manuals will include specific instructions on adapting each posture and/or using props to accommodate problems with mobility, flexibility, or balance. To promote quality and safety, the instructors leading classes will be required to have at least 2 years of experience teaching yoga and have completed dedicated, study-specific training with the study's expert consultants. Following procedures established in the pilot study, a consultant will visit at least one class in each series to ensure that postures are being taught according to protocol, evaluate students' success in learning yoga, and ensure fidelity across instructors. Twice monthly conference calls will be conducted to help instructors trouble-shoot issues that arise in instruction.

Post-intervention program continuation: After the end of the main 12-week intervention period, participants will be encouraged to continue to practice yoga at least two hours per week at home, although group intervention classes will no longer be offered through the study.

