6.1.8 Additional Screening and Covariate Measures

The following data will be collected to assess eligibility, assess whether treatment groups are comparable at baseline, and guide statistical adjustments in the event groups are not balanced:

- A. Demographic history including date of birth, gender/sex identity, race/ethnicity, education history, employment history, marital status (screening/baseline)
- B. Urologic/urogynecologic history including age of onset of incontinence, past and current treatment of incontinence, history of pelvic surgery, history of pregnancy and delivery, menstrual/menopausal status, sexual activity status (screening/baseline)
- C. General medical history including general health assessed by the CDC Healthy Days module,⁹¹ selected medical conditions associated with incontinence such as diabetes, tobacco and alcohol use, and physical activity level (screening)
- D. Current medication use (screening/baseline and 12 weeks)
- E. Health-related habits such as tobacco/alcohol use (screening); fluid and caffeine intake using the fluid intake amount and fluid intake behavior sections of the Questionnaire-Based Voiding Diary⁹²⁻⁹⁴ (baseline, 6 weeks, 12 weeks, and 12 and 24 weeks post-intervention); prior yoga experience, prior group-based physical activity instruction (screening), physical activity level by the International Physical Activity Questionnaire^{95,96} (screening)
- F. Sleep function assessed using the Pittsburgh Sleep Quality Index (PSQI),^{97,98} a validated questionnaire evaluating sleep quality, latency, efficiency, and problems, and a the Pittsburgh Sleep Diary, a daily self-report measure of sleep duration and disruption used to enhance or complement data obtained from actigraphy in multiple past studies of older adults⁹⁹⁻¹⁰¹ (baseline, 6 weeks, and 12 weeks, as well as 12 and 24 weeks after the end of intervention programs).
- G. Physical exam measures including measured height, weight, heart rate, and blood pressure (screening/baseline and 12 weeks)

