9.2 Sample Size

Sample size has been calculated based on parameter estimates derived from both the investigators' past pilot studies on yoga as well as other group-based incontinence intervention trials conducted by study team members.¹⁰³ Assumptions include: a) average baseline frequency of incontinence of ~23-24 episodes/week; b) standard deviation (SD) of change in incontinence frequency of ~14.4; c) correlation between outcome values of ~0.59; and d) loss of ~15% by 3 months. Assuming a ~50% decrease in incontinence frequency among controls (which is the threshold at which women with daily incontinence start to perceive meaningful benefit from treatment¹⁸), the team will power the study to detect a between-group difference in reduction in incontinence of at least 20% in the yoga versus stretching/strengthening control group (corresponding to a \geq 70% reduction in frequency of incontinence in the yoga group) at 3 months. Under these assumptions, a sample size of 240 (120 per group) will provide 80% power in 2-sided tests with 5% type-I error to detect a between-group difference in reduction in the primary outcome of total incontinence frequency of at least 20% in the yoga vs. control arm. With regard to secondary outcomes, this sample will also provide 80% power to detect moderate between-group differences of 0.26 to 0.39 SDs, assuming intraclass correlation of outcomes in the range of 0.4-0.8.

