Exploratory subgroup analyses. Intervention effects will be analyzed in subgroups in multivariate analysis based on a limited set of clinicopathologic factors that are hypothesized to have the potential to influence participants' response to the yoga and stretching/strengthening interventions. For example, we may explore whether baseline participant age, race/ethnicity, clinical type of incontinence, pelvic floor muscle strength, or physical function levels influence subsequent treatment-associated changes in primary and secondary outcomes. Subgroup-specific effects, estimated using the interaction model, will be presented only if the interaction between treatment and subgroup is statistically significant at $p < 0.05$.

During the COVID-19 pandemic, intervention instruction in some study waves may be converted to remote platforms (i.e., interactive video-based class instruction rather than in-person class instruction). In that event, we will use the methods outlined above for exploratory subgroup analyses to evaluate differences in the effect of the intervention in waves that rely primarily on video-based instruction rather than in-person instruction.

Co-intervention effects. Because awareness of intervention assignment can affect use of co-interventions, women in both groups will be asked to refrain from using other clinical incontinence treatments during the study. Nevertheless, information about co-interventions will be collected at follow-up visits to permit assessment of potential effects of differential use of co-interventions on outcomes. To estimate the direct effect of the intervention in the absence of co-interventions, we may conduct additional analyses to add co-intervention use, as well as confounders of its effect on the outcome, to the primary treatment model; if factors that are also affected by the co-interventions are among the confounders, we may use inverse weighting rather than direct adjustment for this purpose.

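### The protocol discourages non-study yoga only in the yoga arm, and through week 12 it has no dedicated measure of outside classes, so control uptake could dilute the effect and be only partly detected

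*Combined protocol and SAP*

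**What the plan says.** **At entry.** Section 4.2 excludes women who attended organised yoga, or organised stretching/strengthening classes, at least weekly in the past 3 months.

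**After randomisation, both arms.** Section 5.3.2 states: "Participants will be asked to refrain from using other standard clinical treatments for incontinence during the 12-week intervention period". The list that follows covers drugs, invasive or surgical treatment, nerve stimulation, devices and practitioner-led behavioural programmes. Use of these in the 12 weeks is recorded as a protocol deviation. The co-intervention paragraph in section 9.6.2 has the same scope: "women in both groups will be asked to refrain from using other clinical incontinence treatments during the study".

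**After randomisation, yoga arm.** Section 5.1 (Home practice) discourages participants "from taking part in non-study yoga activities that might dilute study techniques".

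**After randomisation, control arm.** The home-practice and continuation paragraphs of section 5.2 contain no corresponding sentence.

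**Measurement.** Section 6.1.8 lists "prior yoga experience, prior group-based physical activity instruction (screening", that is, at screening only; physical activity level is also collected at screening. The table in section 6.2.7 schedules a co-intervention assessment at weeks 6 and 12 and at both post-intervention assessments. Section 6.2.5 describes an open question at each of these times about other ways of managing incontinence. At weeks 24 and 36 it adds a question about continued practice of yoga or stretching/strengthening.

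**The concern.** The plan guards the yoga arm against other styles of yoga, but does not state a safeguard against the control arm receiving the kind of activity under test. As written, a control woman who joins a community yoga class departs from no stated request, and no deviation is recorded.

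Such uptake is foreseeable on the protocol's own account. Participants cannot be blinded (section 6.2.4), they are told the study compares yoga with physical conditioning for incontinence (section 5.2), and section 9.6.2 accepts that knowing one's assignment can change the use of co-interventions. The control programme was designed to avoid engaging the pelvic floor or promoting mindful relaxation (section 5.2), and the study postures are described as common in yoga practice generally (section 5.1). An outside class could therefore supply part of what the control is meant to withhold.

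The primary analysis is by intention to treat (section 9.6.1), so any benefit control women gain this way moves the estimated difference towards zero. If uptake is only partly recorded, the co-intervention analysis in section 9.6.2 can only partly describe it.

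**Working it through.** **Inputs (section 9.2).** The plan states that "a sample size of 240 (120 per group) will provide 80% power in 2-sided tests with 5% type-I error". It assumes "average baseline frequency of incontinence of ~23-24 episodes/week", "standard deviation (SD) of change in incontinence frequency of ~14.4", "correlation between outcome values of ~0.59" and about 15% loss by 3 months. The target is a 20-point difference in percentage reduction, which is 0.20 × 23 = 4.6 to 0.20 × 24 = 4.8 episodes/week.

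**Step 1: reproduce the plan's 240.** Reduce the SD of change for baseline adjustment: 14.4 × √(1 − 0.59²) = 11.63.

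- Per arm: n = 2 × (1.960 + 0.842)² × 11.63² / 4.6², rounded up to 101.
- After loss: 101 / 0.85, rounded up to 119 per arm, or 238 in total. This matches 240 closely.
- With 120 × 0.85 = 102 evaluable per arm, power is 80.7% at baseline 23, 82.3% at 23.5 and 83.9% at 24.

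The stated size therefore corresponds to the low end of the baseline range. Section 9.2 mentions no allowance for control women taking up yoga.

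**Step 2: dilution.** Let c be the share of control women who take up outside yoga and f the fraction of the yoga-control difference they gain. Neither is in the documents; both are assumptions. The expected difference becomes Δ × (1 − c·f), with the SD held fixed. Starting from exactly 80% power:

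power = Φ[(1 − c·f) × 2.802 − 1.960]

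- c·f = 0.05: Φ(0.702) = 76%
- c·f = 0.10: Φ(0.562) = 71%
- c·f = 0.20: Φ(0.282) = 61%

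With f = 1 these are uptakes of 5%, 10% and 20%. With f = 0.5, uptakes of 10% and 20% give c·f = 0.05 and 0.10, hence 76% and 71%.

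**Step 3: the same with 102 evaluable per arm.**

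| c·f | Difference, baseline 23 | Power, baseline 23 | Power, baseline 24 | Total N for 80%, baseline 23 |
|---|---|---|---|---|
| 0 | 4.60 | 80.7% | 83.9% | 238 |
| 0.05 | 4.37 | 76.6% | 80.0% | 264 |
| 0.10 | 4.14 | 72.0% | 75.6% | 292 |
| 0.20 | 3.68 | 61.8% | 65.5% | 370 |

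**Step 4: what the scheduled questions can detect.**

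- Weeks 6 and 12: the question concerns managing incontinence. Yoga taken up for that purpose could be reported; yoga for fitness or stress could be missed.
- Home practice logs (section 5.4): these record home sessions of poses or exercises and are not described as covering outside classes.
- Weeks 24 and 36: yoga is named, but as continued practice, which reads as the assigned programme, and after the 12-week endpoint.

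**The case against.** A reader might infer that yoga uptake is not measured at all after screening, that crossover would go unseen, and that a null result could not be interpreted. The documents do not support this. Co-interventions are assessed four times in both arms. Women who enrolled because of incontinence and know yoga is the comparator could well name it when asked how else they manage their symptoms. Section 9.6.2 already foresees an analysis using these data. The intention-to-treat estimate also remains a valid effect of assignment, and the attenuation runs in a known direction.

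Nor do the documents show that control women are never asked to avoid yoga. The control manual, the orientation content and the co-intervention form are not included; only the protocol's silence can be established.

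The size is also open to challenge. The uptake rates are assumed. Full effect is an upper bound, because the study programme is a pelvic-floor-directed set of 16 postures taught by specially trained instructors, and a general class taken for fitness is unlikely to match it. Control women already give about four hours a week (two 90-minute classes plus one hour at home), which limits room for more. After week 12, section 5.3.2 steers both arms towards continued practice of their own programme, which partly protects the persistence comparison.

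These points stand and limit the claim. They do not remove the difference between arms in what the protocol asks, or supply a question that would reliably pick up outside classes before the primary endpoint.

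**Conclusion.** The point holds in a limited form. The protocol states a discouragement of non-study yoga for one arm only, and through week 12 it relies on a generic question that may miss part of any control uptake. Uptake would attenuate the primary difference and make a null result harder, though not impossible, to interpret.

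The true size is unknown. Under the full-effect upper bound and 80% starting power, the loss is about 4 percentage points at 5% uptake, 9 at 10% and 19 at 20%; at half effect, 10% and 20% uptake cost about 4 and 9 points. If baseline frequency is 23.5 to 24 episodes/week, starting power is somewhat higher and absorbs part of this: at 24, 5% uptake with full effect still leaves 80.0%. All these figures inherit the basis of section 9.2 and hold the SD fixed.

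This is a gap in conduct and data capture, not a contradiction or an error in the analysis. It is worth closing because outside classes not recorded during the trial are unlikely to be recovered afterwards.

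**What to change.** 1. In sections 5.2 and 5.3.2, extend the discouragement of non-study yoga already in section 5.1 to the control arm, so that both arms receive the same request during the 12-week intervention. Carry it into the participant materials if it is not already there.
2. Add one fixed item to the existing co-intervention assessment at weeks 6, 12, 24 and 36, in both arms: any non-study yoga or organised exercise classes, with type and hours per week.
3. Report uptake by arm, and name it in section 9.6.2 as an input to the co-intervention analysis. The intention-to-treat primary analysis stays as it is.

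The cost is one small extra request to participants and one item on a form already in use. The item is useful even without the request, because it makes uptake visible.
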